#### 8.5.2 Censoring at Study Completion

8.5.2.1 Censoring for MACE, MACE+, each Component of MACE, and All-Cause Mortality

If non-inferiority between lorcaserin HCl and placebo is confirmed at the interim analysis, then the study will be continued to observe; 1401MACE+ events at approximately 54 months from the start of the study and 2.5 years median treatment duration.

algorithms

MACE non-inferiority and superiority, each component of MACE, and All-cause mortality will analyzed at study completion as part of additional sensitivity analyses. The censoring algorithm is the same for these endpoints but differs by Analysis Set as described in the Table 6, and see Appendix 13.2 for diagrams of censoring algorithms.

For subjects who experienced an event, their time-to-event will be determined from the randomization date (for the Total Time Analysis) and the start date of study drug (for the On-Treatment and On-Treatment + 30-Days Analyses), to the date of the event. The censoring variable will be, CENSORED=0. For subjects who do not experienced an event, the censoring time will be determined from the randomization date (for the Total Time Analysis) and the start date of study drug (for the On-Treatment and On-Treatment + 30-Days Analyses), to the date described in Table 6, along with a matching censoring variable, CENSORED=1.

Table 6 Censoring Date For subjects who did not experienced an event at Study Completion

Table o Ce	ensoring Date For subjects who did not ex	xperienced an event at Study Completion
Analysis		
Set a	Completed the Study	Withdrawal From Study Follow-up
Total Time	In the Final Study Disposition Form use	In the Final Study Disposition Form use the
on Study	the date from , Date of Final Sponsor	date from , Date of Final Sponsor
	Notification/Premature Study	Notification/Premature Study Discontinuation
	Discontinuation	and
	and status is equal to completed	status for discontinuation equals any of the
		following;
		Withdrew Consent
		Lost to Follow up
		Study Terminated by Sponsor
		• death (except for All Cause-mortality)
		• Other
On-	Date of last dose from Study	Date of last dose from Study Medication Form
Treatment +	Medication Form + 30 Days	+ 30 Days
30 Days		
-		
On-	Date of last dose from Study Medication	Date of last dose from Study Medication Form
Treatment	Form	
a See Section	5.2.1 for definitions of Analysis Sets and A	Appendix 13.5.2 for diagrams of censoring

algorithms

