9.7.1.2 Definitions of Analysis Sets

The Safety Analysis Set will be the group of subjects who received at least 1 dose of study drug and had at least 1 postdose safety assessment.

The Intent-to-Treat set (ITT) will be the group of all randomized subjects regardless of whether they took study drug or not.

- Total Time Analysis Set: Using the ITT, events are counted that occur while subjects are on and off treatment. Subjects with no events who discontinue early or complete the study will be censored at their last study contact (see details in the SAP). This will be used for the primary analysis.
- On-Treatment plus 30 Days Analysis Set: Using the ITT, events are counted that occur while subjects are on treatment and up to 30 days from their last dose. Subjects with no events who discontinue early or complete the study will be censored at their last dose day plus 30 days.
- On-Treatment Analysis Set: Using the ITT, events are counted that occur while subjects are on treatment. Subjects with no events who discontinue early or complete the study will be censored at their last dose day.
- Prediabetes Analysis Set: This set includes all subjects in the ITT set without a history of any type of diabetes and who are prediabetic at Baseline. Definition of prediabetes will be found in the SAP. (revised per Amendment 01)
- Nondiabetes Analysis Set: This set includes all subjects in the ITT set without a history of any type of diabetes at Baseline. Definition of nondiabetes will be found in the SAP. (revised per Amendment 01)

T2DM Analysis Set: This set will be all subjects in the ITT who have T2DM at Baseline.

FDA-defined Valvulopathy Analysis Set: This set will be all subjects in the ITT without FDA-defined valvulopathy at Baseline. The data from this study will be pooled with the data from the 3 pivotal lorcaserin HCl studies (APD356-009, -010, and -011).

The PD Analysis Set will be the group of subjects who have both baseline and at least 1 postbaseline assessment of at least 1 PD parameter.

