## 5.2 STUDY SUBJECTS

#### **5.2.1** Definitions of Analysis Sets

The number (percent) of subjects included in each analysis set will be presented by analysis set, treatment group and overall. The description of the analysis data sets are:

- The Safety Analysis Set: will be the group of subjects who received at least one dose of study drug and had at least one post dose safety assessment.
- The Intent-to-Treat (ITT) Set: will be the group of all randomized subjects regardless of whether they took study drug or not. This is the same as the Full Analysis Set.
- Total Time Analysis Set: Using the ITT, events are counted that occur while subjects are on and off treatment. Subjects with no events will be censored at their last study contact or at the visit following Sponsor Notification of Study Completion, whichever

- occurs first. This analysis set will be used for the primary analysis. See Section 8.5 for censoring algorithm.
- On-Treatment plus 30 Days Analysis Set: Using the ITT, events are counted that occur
  while subjects are "on treatment" and up to 30 days from their last dose. Subjects with
  no events who discontinue early or complete the study will be censored at their last dose
  date plus 30 days. See Section 8 for definition of "on treatment" and Section 8.5 for
  censoring algorithm.
- On-Treatment Analysis Set: Using the ITT, events are counted that occur while subjects are "on treatment". Subjects with no events who discontinue early or complete the study will be censored at their last dose date. See Section 8 for definition of "on treatment" and Section 8.5 for censoring algorithm.
- Prediabetes Analysis Set: This set includes all subjects in the ITT set without a history of any type of diabetes and who are prediabetic at Baseline (defined in Section 8).
- Nondiabetes Analysis Set: This set includes all subjects in the ITT set without a history of any type of diabetes at Baseline (defined in Section 8).
- T2DM Analysis Set: This set will be all subjects in the ITT who have T2DM at Baseline (defined in Section 8).
- FDA-defined Valvulopathy Analysis Set: This set will be all subjects in the ITT without FDA- defined valvulopathy at Baseline (defined in Section 8.4). The data from the ECHO sub-study will be pooled with the ECHO data from the 3 pivotal lorcaserin HCl studies (APD356-009, APD356-010, and APD356-011).

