#### 5.2.2 Subject Disposition

The number of subjects screened and the number (percent) of subjects who failed screening and the reasons for screen failure will be summarized, based on data reported on the Screening Disposition CRF. The distribution of the number of randomized subjects enrolled by each site will be summarized for each randomized treatment group. The primary reasons for screen failures; did not meet inclusion/exclusion criteria, AE, lost to follow-up, withdrawal of consent, and other, will be presented.

For study completion, the number (percent) of randomized subjects who completed the study (e.g. subject was in the study at the date of Final Sponsor Notification/Premature Study Discontinuation by Sponsor, whether subject is on or off treatment or death) and who

discontinued from the study will be summarized according to the primary reason for discontinuation based on data reported on the Final Study Disposition CRF. The number (percent) will be presented by treatment group and total for subjects; randomized, not treated, treated, who completed the study, and discontinued from the study. For those who are considered to have discontinued from the study, the reasons for discontinuation from the study at Final Sponsor Notification/ Premature Study Discontinuation are captured in the Final Study Disposition CRF (Withdrawal of Consent, Lost to follow up, Study prematurely terminated by sponsor, and Other).

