#### 8.5 CENSORING

The individual EOS date will be defined as the time of the last visit or study contact for each individual patient. If no event occurs for an endpoint, the earlier of the last study contact, the visit following Sponsor Notification of Study Completion or death will be treated as the censoring date.

MACE, MACE+ and conversion to T2DM events will be handled in the following manner according to their timing with respect to study milestones:

- Events that are recorded as beginning prior to the date of randomization will not be counted in the event analyses. The subject will be included in the analysis as not experienced the event. These events that are recorded as beginning prior to the date of randomization they will be included in a listing.
- Events that occur at any time after randomization and up to and including the first of the last visit/contact or visit following Sponsor Notification of Study Completion and reported *before* database lock will be adjudicated and included in all efficacy and safety analyses.
- Events that occur at any time after randomization and up to and including the last visit/contact and reported *after* database lock will be not be adjudicated and will not be included in the primary efficacy and safety analysis. They will be recorded in a tabular fashion as part of the final study report and may be included in sensitivity analyses.
- Events that occur after last visit/contact will not be included in the primary efficacy and safety analyses but may be included in the safety database if they fulfill safety reporting criteria.

Events in subjects who withdraw consent for clinical follow-up:

- All events that occur before withdraw of consent are included in analyses.
- Events that occur after withdraw of consent will be included in the primary analyses if they were found through vital status search prior to database lock.

Events in subjects who stop and re-start study medication.

• For the Total Time Analysis Set all events are counted regardless of whether the subject is on or off treatment.

- For the On-treatment Analysis Set events are counted only when the subject in "on-treatment". See Section 8, for definition of "on-treatment".
- For the On-treatment plus 30 days Analysis Set events are counted when the subject is "on-treatment" and up to 30 days from their last dose. See Section 8, for definition of "on-treatment".

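### For lost subjects and non-endpoint deaths, SAP Table 6 replaces last-contact or death-date censoring with an undefined disposition-form date, which could add risk time in which no MACE+ event can count

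*SAP*

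**What the plan says.** **General rule.** SAP 5.2.1 defines the Total Time Analysis Set: "Subjects with no events will be censored at their last study contact or at the visit following Sponsor Notification of Study Completion", whichever comes first. SAP 8.5 adds death: "the earlier of the last study contact, the visit following Sponsor Notification of Study Completion or death will be treated as the censoring date". The same section ties end of study to contact: "The individual EOS date will be defined as the time of the last visit or study contact for each individual patient". Protocol 9.7.1.2 also uses last study contact and leaves the detail to the SAP.

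**Event window.** For MACE, MACE+ and T2DM conversion, SAP 8.5 states: "Events that occur after last visit/contact will not be included in the primary efficacy and safety analyses". It makes one exception, for events found by vital-status search in subjects who withdrew consent.

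**Endpoint-specific rule.** SAP 8.5.2.1 sends subjects without an event "to the date described in Table 6, along with a matching censoring variable, CENSORED=1". In the Total Time row, Table 6 takes the Final Study Disposition form date for final sponsor notification or premature study discontinuation. Its withdrawal column names lost to follow-up, withdrawn consent, termination by the sponsor, death (except for all-cause mortality) and other.

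**Reach.** Total Time is the primary set for MACE+ (SAP 5.4.1). T2DM conversion, the key secondary endpoint, takes its censoring date from Table 6 through 8.5.2.2. Table 7 uses the same form date for the renal and glucose-homeostasis endpoints.

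**The concern.** Two parts of the SAP give different censoring dates for the same subjects in the confirmatory MACE+ analysis. A programmer working from 8.5 and one working from Table 6 could build different datasets, and each would be following the plan.

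The difference matters if the form date is later than last contact. A lost subject would then stay in the risk set after the event window has closed. The denominator grows, the numerator cannot, and event rates are understated. If the arms lose subjects at different rates, the hazard ratio moves in favour of the arm that loses more.

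A late date is a fair reading. SAP 5.2.2 says "the reasons for discontinuation from the study at Final Sponsor Notification/ Premature Study Discontinuation are captured in the Final Study Disposition CRF", and its definition of study completion attributes premature study discontinuation to the sponsor, which suggests a study-wide date. Table 5, the interim counterpart, does not list lost to follow-up, which suggests that this status may be assigned only at close-out.

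Deaths that are not endpoints raise the same issue: Table 6 uses the form date where 8.5 uses the death date.

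**Working it through.** **1. The rules side by side, Total Time set, no event**

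| Subject | SAP 8.5 | Table 6 |
|---|---|---|
| Lost to follow-up | last contact | form date |
| Non-endpoint death | death, if earliest | form date |
| MACE+ event after last contact | not counted | no separate provision |

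Neither document equates the form date with last contact.

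**2. The plan's own figure.** Inputs from SAP 4 and protocol 9.7.2: 1401 MACE+ events, hazard ratio 0.85, two-sided alpha 0.05, 1:1 allocation. Power = Φ(|ln 0.85| × √1401 / 2 − 1.96) = Φ(0.1625 × 18.715 − 1.96) = Φ(1.08) = 86.0%, against a stated figure above 85%. It reproduces, so the design arithmetic is not in question.

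**3. Upper bound on the effect.** From the documents: 12,000 subjects (6,000 per arm), placebo hazard 0.035 per year, 15-month accrual (taken as uniform), 54 months in total. Assumed, because the documents give neither figure: the lost-to-follow-up rate d in each arm, and a form date at study end for every lost subject. Events and loss are exponential and independent. Non-endpoint deaths are not modelled.

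Let G(t) be the fraction of subjects whose calendar follow-up reaches t, n the number per arm and λ the arm's event hazard. In each arm:

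- Events, the same under both rules: n·G(t)·λ·exp(−(λ+d)t)
- At risk, last-contact rule: n·G(t)·exp(−(λ+d)t)
- At risk, form date at study end: n·G(t)·[1 − λ/(λ+d)·(1 − exp(−(λ+d)t))]

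The large-sample Cox estimate solves the score equation with these quantities. Person-years (PY) are at a true hazard ratio of 0.85.

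| Loss/yr, placebo / lorcaserin | PY to last contact | Added PY | Added | HR if true 0.85 | HR if true 1.00 |
|---|---|---|---|---|---|
| 0.5% / 0.5% | 43,265 | 433 | 1.0% | 0.8501 | 1.000 |
| 1% / 1% | 42,856 | 860 | 2.0% | 0.8501 | 1.000 |
| 2% / 2% | 42,052 | 1,699 | 4.0% | 0.8502 | 1.000 |
| 5% / 5% | 39,763 | 4,090 | 10.3% | 0.8505 | 1.000 |
| 1% / 2% | 42,451 | 1,281 | 3.0% | 0.8336 | 0.9805 |
| 5% / 6% | 39,398 | 4,470 | 11.3% | 0.8345 | 0.9811 |
| 3% / 5% | 40,511 | 3,305 | 8.2% | 0.8182 | 0.9620 |
| 5% / 7% | 39,042 | 4,840 | 12.4% | 0.8189 | 0.9626 |
| 5% / 3% | 40,521 | 3,300 | 8.1% | 0.8840 | 1.0395 |

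At 5% loss in both arms the placebo rate falls from 3.50 to 3.17 per 100 person-years. Under last-contact censoring every row returns the true hazard ratio.

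**4. What this does to the test at 1401 events.** With a true ratio of 1.00, two-sided rejection is about 6.5% when loss is 1 point per year higher on lorcaserin and about 11% when it is 2 points higher. With a true ratio of 0.85 and loss 2 points higher on placebo, power is Φ(|ln 0.884| × 18.715 − 1.96) = about 64%.

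**The case against.** The strongest reply is that the form date may well be each subject's own. The field has two parts, and Table 5 uses it for individual withdrawals at the interim, before any final notification exists, so it can hold an earlier date. Three places already state last contact, and Table 6's footnote refers back to 5.2.1. SAP 5.4.1.1 plans multiple imputation for lost subjects, which would have little or nothing to impute if they already ran to study end. The censoring diagrams that Table 6 cites are not reproduced in the public copy. A lost subject who is traced may also gain a new last contact, which moves the event window and the censoring date together.

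All of this stands as evidence of what was probably intended, and it means the effect may be zero. It does not remove the conflict, because the specific table still names a date that nothing defines for lost subjects.

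Three stronger readings are not supported:

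- **That deaths traced in lost subjects are dropped from all-cause mortality.** The exclusion in 8.5 is introduced for MACE, MACE+ and T2DM conversion only. Table 6 treats all-cause mortality separately in its death entry, and no text says such deaths are discarded.
- **That the MACE+ hazard ratio is biased toward lorcaserin.** The documents give no loss rate and no imbalance. With equal loss the ratio is essentially unchanged, and more loss on placebo pushes it the other way.
- **That the primary MACE noninferiority test runs on Table 6.** It is done at the interim under Table 5; MACE at completion is a sensitivity analysis.

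**Conclusion.** The conflict is real and affects the primary MACE+ analysis. It also reaches the key secondary T2DM analysis and the completion MACE sensitivity analyses. The body sentence of 8.5.2.1 omits MACE+, but the section heading includes it.

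The size of the effect is unknown. It is nil for lost subjects if sites enter last contact on the form. The tabulated results are an upper bound that rests on study-end form dates and non-informative loss; the 10% figure also needs the whole planned drop-out to be lost to follow-up, and any shift in the hazard ratio of note needs unequal loss. The statement that no event can count applies to lost subjects, not to those who withdrew consent, for whom the vital-status exception exists. Because the wording bears on a confirmatory test and any bias would depend on differential loss, it should be settled before unblinding.

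**What to change.** In the Total Time row of Table 6, and likewise in Table 7, replace the form date by the date of last study contact at which endpoint status was ascertained, or the date of death if earlier, capped at the visit following Sponsor Notification of Study Completion. The tables then agree with SAP 8.5 and 5.2.1. T2DM conversion follows automatically through 8.5.2.2, and the Appendix 13.2 diagrams should be checked against the same rule.

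The cost is a wording change in two tables and one derived date. Visits and follow-up contacts are already recorded in the CRF, so no new data collection is needed.

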#### 8.5.2.2 Censoring for Conversion to T2DM

For subjects who experienced an event, their time-to-event will be determined from the randomization date to the date of first abnormal laboratory test as per the Diabetes CEC Diabetes Adjudication Charter, Appendix 13.1.4. The censoring variable will be, CENSORED=0. For subjects who do not experienced an event, the censoring time will be determined from the randomization date to the date described in the Table 6, using the Total Time on Study Analysis Set, along with a matching censoring variable, CENSORED=1. The above censoring algorithm

will be applied to both cohorts 1) subjects without any type diabetes at Baseline and 2) subjects with prediabetis at Baseline.

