All subjects will continue in the study until study completion, rather than for a prespecified number of visits. Subjects who prematurely discontinue study drug will continue in the study for all subsequent study visits until study completion and are to complete visit procedures as indicated in [Table 4](#). It is preferred that these visits are in person. However, if the subject is unable to attend a visit in person, a telephone visit may be performed. The outcome of the telephone visit must be clearly documented in the source record. At a minimum, the site should attempt to have the subject return for an in-person visit at least once per year. The study will terminate when 1401 MACE+ events have occurred and when there has been a median treatment duration of 2.5 years have accrued. (revised per Amendment 02) This is expected to occur on or before October 2018.

When 460 adjudicated MACE events have occurred, an interim analysis will be conducted on MACE events (see [Section 9.7.3](#)). It will be conducted to establish whether the primary safety objective (MACE noninferiority) has been achieved. This analysis will be performed by an independent statistician and governed by an independent Data Monitoring Committee (DMC) and is anticipated to occur on or before (approximately) July 2017. (revised per Amendment 02). If the primary safety objective has been achieved, the trial will continue for evaluation of additional endpoints as delineated in the objectives.

An overview of the study design is presented in [Figure 1](#).

[figure not shown]

Figure 1 Study Design Schematic

BID = twice daily; EOS = end of study; EOT = end of treatment; R = randomization.

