- b. Assessments are only to be performed if clinically indicated or necessary due to state controlled substance requirements. (revised per Amendment 01)
- c. Window ±10 days for all visits after Visit 2, other than the EOS visit which has a window of +10 days. Month is shown unless otherwise indicated; 1 month = approximately 30 days.
- d. Only for a subset of subjects at selected sites. Baseline echocardiograms will be performed in between Visits 1 and 2, after the results of screening assessments have been obtained but prior to randomization, and subject eligibility is confirmed. ECHOs will be performed until at least 1000 subjects have completed the Month 36 echocardiographic assessment. (revised per Amendment 02)

Table 4 Schedule of Procedures/Assessments in Study APD356-G000-401

Phase	Pre-randomization	Randomization																		
Period	Screening	Treatment																	F/U	
Visit	1	2 ^a	3	4	5	6	7	8	9	10	11	12	13	14	15	16	17	EOT	EOS	Unsch ^b
Month ^c	Days -30 to -1	Day 1	3	6	9	12	15	18	21	24	28	32	36	40	44	48	52	56		
Assessment (revised per Amendment 01)																				

- e. For subjects who discontinue study drug early, these assessments will be stopped after the EOT visit.
- f. Renal function parameters and glycemic profile should be obtained at all specified visits, regardless of study drug status. (revised per Amendment 01)
- g. Serum cystatin C will be measured at Baseline and yearly thereafter in the subpopulation with CKD Stage 1 or 2 at Baseline. Serum creatinine will be measured in chemistry blood samples if chemistry assessments are performed.
- h. Serum pregnancy tests will be conducted at Screening. A urine pregnancy test will be conducted at randomization.
- i. These assessments should be done if a telephone contact is performed in lieu of a clinic visit.

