#### 8.5.2.3 Censoring for Secondary Time-to-Event Endpoints

The censoring algorithm is the same for all secondary time-to-event endpoints and across the different Analysis Sets. Since all the Analyses Sets used the ITT population for these secondary endpoints, then for subjects who experienced an event, their time-to-event will be determined from the randomization date to the date of the event. The censoring variable will be, CENSORED=0. For subjects who do not experienced an event, the censoring time will be determined from the randomization date to the date described in Table7, along with a matching censoring variable, CENSORED=1.

Table 7 Censoring Date for Subjects who did not Experience an Event at Study Completion for Secondary Renal and Clucose Homeostasis Endnoints

Secondary Renal and G	lucose Homeo	stasis Endpoints	
	Analysis		Withdrawal From Study Follow-
Time-to-Event Endpoint	Set a	Completed the Study	up
New onset of renal	T2DM	In the Final Study	In the Final Study Disposition
impairment or		Disposition Form use the	Form use the date from, Date of
worsening of existing		date from;	Final Sponsor
renal impairment in		Date of Final Sponsor	Notification/Premature Study
subjects with T2DM at		Notification/Premature	Discontinuation
Baseline		Study Discontinuation	and
New onset of renal	Total Time	and status is equal to	status for discontinuation equals
impairment or		completed	any of the following;
worsening of existing			Withdrew Consent
renal impairment in all			Lost to Follow up
subjects enrolled in the			Study Terminated by Sponsor
study			• Death
Improvement in renal	T2DM		• Other
function	12DNI		
Tunction			
New onset of renal	Prediabetes		
impairment or	riediabetes		
worsening of existing			
renal impairment in			
subjects with			
prediabetes at Baseline			
Conversion to normal	Prediabetes		
glucose homeostasis	1 iculaucies		
a See Section 5.2.1 for det	finitions of An	alvsis Sets	1
500 50000011 5.2.1 101 del	11111110110 01 7 1111	11 J D 10 D D 0 0	

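### SAP 8.5.2.2 and 8.5.2.3 censor laboratory-detected endpoints at the final disposition date, not the last test, so untested follow-up counts as event-free

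*SAP*

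**What the plan says.** **Conversion to T2DM (SAP 8.5.2.2).** With an event, time runs from "randomization date to the date of first abnormal laboratory test". Without an event, "the censoring time will be determined from the randomization date to the date described in the Table 6", Total Time row. That row of Table 6 reads "In the Final Study Disposition Form use the" date of sponsor notification or premature discontinuation. It applies to completers and to subjects who withdrew, were lost or died.

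**Renal and normal-glucose endpoints (SAP 8.5.2.3).** "The censoring algorithm is the same for all secondary time-to-event endpoints and across the different Analysis Sets". Table 7 uses the same disposition-form date.

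**General rule (SAP 8.5).** "If no event occurs for an endpoint, the earlier of the last study contact, the visit following Sponsor Notification of Study Completion or death" sets the censoring date. The last HbA1c, FPG, ACR or creatinine is not mentioned in any of these sections.

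**Follow-up without tests (Protocol 9.1 and Table 4).** "if the subject is unable to attend a visit in person, a telephone visit may be performed". Footnote i says "These assessments should be done if a telephone contact is performed in lieu of a clinic visit", and it is attached to concomitant medications, AE monitoring and MACE/MACE+ reporting. No laboratory row carries it.

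**Test schedule (Protocol Table 4).** HbA1c is taken every 3 to 8 months, FPG yearly from Month 12 and ACR yearly. All three are also scheduled at EOT and EOS.

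**The concern.** A censoring date should be the last time at which the subject was known to be free of the event. For MACE, a contact can establish that, so the disposition date fits. For an outcome found mainly by a blood or urine test, a telephone contact usually cannot. The event is tied to a test and the censoring date is not. Time after the last test therefore adds to the risk set while few events can enter from it.

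Conversion to T2DM in prediabetes is the key secondary endpoint and the last step of the gatekeeping procedure (SAP 5.3.3). SAP 5.4 also promises event rates per 100 patient-years, which this time dilutes even when the arms are balanced. The telephone provision is written for subjects who have stopped study drug, and stopping may differ by arm.

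No planned analysis censors at the last test. The T2DM sensitivity analyses use the On-Treatment sets, which Table 6 censors at last dose or 30 days later. Multiple imputation for lost subjects (SAP 5.4.1.1) covers only MACE superiority and MACE+.

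**Working it through.** **1. The plan's own figure.** Inputs from SAP section 4: 457 events, HR 0.75, two-sided alpha 0.05, 4% per year, 5% per year drop-out, 15-month accrual, 54 months, and 33% of 12,000 = 3,960 prediabetic subjects randomized 1:1.

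- Power (Schoenfeld): Φ(√457 / 2 × |ln 0.75| − 1.96) = Φ(1.115) = 86.8%. Freedman's formula gives 86.3%. The plan states 86%.
- Events per arm: n × h/(h+d) × the mean of [1 − exp(−(h+d)(4.5 − s))] over entry time s, uniform on 0 to 1.25 years, where h is the event hazard and d = 0.05. With h = 0.04 and h = 0.03 and 1,980 subjects per arm, the total is 456.5. The plan states 457.

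The sample-size arithmetic reproduces and is not in question.

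**2. Effect on the rate.** The documents give no figure for untested follow-up. Assume that a share u of subjects stops testing at a uniform point of follow-up, stays in contact, and has no event detected afterwards. On average half of such a subject's time is untested, so the rate under the present rule is about 4.0 × (1 − u/2).

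| u, both arms | Formula, per 100 patient-years | Simulated, disposition date | Simulated, last test |
|---|---|---|---|
| 10% | 3.80 | 3.80 | about 4.0 |
| 20% | 3.60 | 3.60 | about 4.0 |
| 30% | 3.40 | 3.40 | about 4.0 |

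The placebo rate is 5%, 10% and 15% too low. The HR is essentially the same under either rule.

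**3. Effect on the HR when testing differs by arm.** Approximately, HR = true HR × (1 − u_L/2) / (1 − u_P/2), with L for lorcaserin and P for placebo. The simulation used 1.5 million subjects per arm and a Cox model.

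| Stop testing, P / L | Formula, true HR 1.00 | Simulated, true 1.00 | Simulated, true 0.75 |
|---|---|---|---|
| 10% / 20% | 0.90/0.95 = 0.947 | 0.947 | 0.709 |
| 20% / 10% | 0.95/0.90 = 1.056 | 1.055 | 0.793 |
| 20% / 25% | 0.875/0.90 = 0.972 | 0.975 | 0.729 |

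Censoring at the last test returns 1.00 and 0.75 within about 0.006. The event count is the same under both rules.

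**4. How far final tests and clinical reports remove the shift.** A second simulation followed the Table 4 HbA1c months under the same design assumptions, with true HR 1.00 and telephone-only shares assumed by arm.

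| Telephone-only subjects | 7% P / 13% L | 10% P / 19% L |
|---|---|---|
| No final test, nothing detected | 0.96 | 0.94 |
| No final test, half of conversions reported | 0.972 | 0.966 |
| Half tested at EOS | 0.975 | not calculated |
| Yearly and EOS tests half attended | 0.995 | 0.977 |
| All completers tested at EOS | 0.996 | 0.994 |

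One-sided false superiority is 6.8% and 10% in the first row and 2.8% and 3.0% in the last, against a nominal 2.5%.

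**The case against.** **Events can surface without a study test.** The T2DM definition includes symptomatic hyperglycemia, and a subject started on antidiabetic drugs after an abnormal preliminary test needs no confirmation. Concomitant medications and AEs are collected by telephone. Dialysis and transplant are captured as SAEs, and renal death is adjudicated. This stands. A reader might infer that no event could be seen once a subject is on telephone follow-up, and the documents do not support that.

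**The protocol works against long untested spells.** Table 4 footnote f asks for renal and glycemic tests at all specified visits regardless of study drug status. Sites should attempt a yearly in-person visit. Subjects still followed return for EOS, and those who withdraw are also to complete EOS procedures. This stands too, and step 4 shows that an attended EOS test removes nearly all of the HR shift. These provisions do not guarantee a test, however, and the censoring date ignores whether one was done.

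**The On-Treatment sensitivity analyses remove most off-drug untested time for T2DM.** This is partly right. They also discard tested off-drug follow-up, so they answer a different question, and the renal endpoints have no such analysis.

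**A rule may exist elsewhere.** The Diabetes Adjudication Charter and the censoring diagrams are not reproduced in the documents reviewed. SAP 8.5.2.2 cites the charter for dating events and sends censoring to Table 6, so the text does not point to another rule, but one cannot be excluded.

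**Conclusion.** The mismatch is in the text: these endpoints are detected mainly by tests, while event-free subjects are credited with time up to a date unrelated to testing. With equal testing by arm the HR is essentially unbiased, and rates per 100 patient-years are about 5-15% too low if 10-30% of subjects stop testing. With a 10-point difference between arms, no final test and no other detection, the HR shifts by about 5-6%. It is near zero if most subjects attend the EOS tests. All stopping shares are assumptions.

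The arm tested less shows fewer events. That flatters it for T2DM conversion and renal worsening, and counts against it for return to normal glucose or renal improvement.

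A reader might infer that the rule favors lorcaserin, or that an HR of about 0.94 to 0.96 under no effect is to be expected. Neither follows. The documents do not say which arm would be tested less, and those values need nearly twice as many telephone-only subjects in one arm, no final test and no clinical detection. Nor are 6.8% and 10% trial-level error rates, because T2DM is tested only after MACE+ succeeds.

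**What to change.** Amend SAP 8.5.2.2 and Table 7 before unblinding:

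- **Conversion to T2DM (both cohorts):** censor event-free subjects at the last HbA1c or FPG.
- **Normal glucose homeostasis:** censor at the last visit with both HbA1c and FPG, because the definition needs both.
- **Laboratory renal components:** censor at the last evaluable ACR or creatinine assessment for that component, allowing for the required two consecutive assessments.
- **Dialysis, renal transplant and renal death:** keep the disposition (last contact) date. A composite has one censoring date per subject, so the SAP should state how the two dates combine.
- **MACE, MACE+ and mortality:** no change.
- **Sensitivity analysis:** keep the present disposition-date rule, counting all adjudicated events, so that events reported clinically after the last test are not lost.
- **Reporting:** give the time from last test to disposition by arm, so that readers can see whether testing was balanced.

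The cost is SAP wording, one extra derivation from test dates already collected, and slightly less person-time.
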